7.2.4. Time Period and Frequency for Event Assessment and Follow-up

AEs will be recorded from the time the informed consent form (ICF) is signed until the end of the follow-up period. AEs will be assessed at each study visit, and participants should be encouraged to contact the study site to report AEs that occur between scheduled visits. AEs that occur in the time period between informed consent and the first dose of study drug of the Treatment Period should be recorded but will not be considered TEAEs.

After the initial AE/SAE report, the Investigator is required to proactively follow each participant at subsequent visits/contacts. All AEs/SAEs will be followed until resolution, stabilization, the event has been shown to be unrelated to study drug, or the participant is lost to follow-up (as defined in [Section 6.3](#)).

7.2.5. Adverse Event Reporting

The Investigator is to report all AEs, whether volunteered by the participant, discovered through questioning, or directly detected, that occur in the time period specified in [Section 7.2.4](#) and according to classifications described in [Section 7.2.3](#).

Non-serious AEs that do not require immediate reporting are to be reported on the AE eCRF. SAEs and AESIs will be reported on the SAE Report Form (see [Section 7.2.6](#)).

Clinically significant AEs such as SAEs, AEs leading to study drug discontinuation/study withdrawal (e.g., based on stopping criteria in [Section 6.1](#)), DLTs ([Section 6.1.1](#)), and AESIs ([Section 7.2.8](#)) that are considered at least possibly related to study drug will be reported to the DMC on an ongoing basis.

7.2.6. Serious Adverse Event Reporting

Throughout the study, the Investigator is to report all SAEs, regardless of suspected causality, to the Sponsor within 24 hours of learning of its occurrence using the SAE Report Form. AESIs (see [Section 7.2.8](#)) will also be reported in the electronic data capture (EDC) system and on the SAE Report Form and must be clearly differentiated from SAEs. Completion guidelines are provided in the Investigator Site File. The Investigator must assess and record the relationship of each event to study drug. Any SAE experienced after the follow-up period should be reported to the Sponsor only if the Investigator suspects a causal relationship to the study drug.

Recurrent episodes, complications, or progression of the initial SAE, regardless of when they occur, must be reported as follow-up to the original episode within 24 hours of the Investigator receiving the follow-up information. Follow-up information will also be captured in the EDC system and should describe whether the event resolved or continues, if and how it was treated, and whether the participant continued or withdrew from study participation. An SAE occurring at a different time interval or otherwise considered completely unrelated to a previously reported SAE should be reported separately as a new event.

The Sponsor will ensure that all SUSARs, determined based on the Reference Safety Information in the most recent version of the IB at the time of the event, will be reported to the FDA and to all Institutional Review Boards (IRBs)/Ethics Committees (ECs) overseeing the conduct of the study, in accordance with FDA 21 CFR 312.32.

7.2.7. Reporting of Pregnancy

Any participant who becomes pregnant during the study will have study drug discontinued immediately and be withdrawn from the study. All pregnancies in female participants or in the female partners of male participants must be reported to the Sponsor within 24 hours of the site learning of the pregnancy. Information about pregnancies will be recorded on the Pregnancy Report Form and any follow-up information will be forwarded to the Sponsor.

For any female participant who becomes pregnant while participating in this study, the Investigator will collect information about the pregnancy and follow up with the participant to determine the outcome of the pregnancy and the status of mother and child.

Male participants will be instructed to notify the site in the event that any female partner becomes pregnant. If any female partner of a male participant who received at least 1 dose of study drug becomes pregnant within 90 days of the male participant's last dose of study drug, the Investigator will attempt to collect information about the pregnancy. The Investigator must obtain informed consent from the pregnant partner before collecting such information. The Investigator will also attempt to follow up with the female partner to determine the outcome of the pregnancy and the status of mother and child.

Generally, follow-up will not be required for longer than 6 to 8 weeks beyond the estimated delivery date. Any termination of the pregnancy will be reported regardless of fetal status (presence or absence of anomalies) or indication for the procedure.

Pregnancy itself is not regarded as an AE. However, a pregnancy complication is an AE, and congenital abnormalities/birth defects or spontaneous miscarriages should be reported as SAEs. Elective termination of a pregnancy is not considered an AE. While the Investigator is not obligated to actively

seek this information in former study participants, he or she may learn of such an SAE through spontaneous reporting.

7.2.8. Adverse Events of Special Interest

AESIs are those AEs (independent of seriousness criteria) that are of specific concern to this study and for which ongoing monitoring and communication with the Investigator and Sponsor may be appropriate. These events will be reported on the SAE Report Form, allowing for the collection of additional information, as warranted. The following may be considered AESIs for this study:

- Significant liver chemistry changes that do not satisfy study drug stopping rules (see [Section 6.1.2](#)). Cases of Hy's Law should be reported as an AESI and SAE.
- Suicidality as indicated by responses on the C-SSRS (see [Section 6.1.5](#) regarding study stopping criteria).
- Depression or anxiety that is moderate or severe (CTCAE Grade 2 or higher), as assessed by the Investigator (see [Section 6.1.6](#) regarding study drug stopping criteria for depression or anxiety). This will be reported as an AESI and if seriousness criteria are met, reported as an SAE.
- Adverse events of adrenal insufficiency are considered AESIs and will be reported on a separate Adrenal Insufficiency Form. Additionally, symptoms of adrenal insufficiency will be reported as SAE if they necessitate parenteral GC administration by a health care professional and two of the following criteria occur or are met: hypotension (systolic blood pressure <90 mmHg); nausea or vomiting; severe fatigue; documented hyponatremia, hyperkalemia, or hypoglycemia. If hospitalization was required or the event of adrenal insufficiency is deemed to be an important medical event, life-threatening, or results in a persistent or significant disability/incapacity or death, it should also be reported as an SAE.
 - For SAEs of adrenal insufficiency, records from the office of the health care provider, emergency facility or hospital should be obtained as source documents to provide the following information:
 - Was stress dosing employed prior to the adrenal insufficiency event? If yes, what were the GC dose and duration of dosing and the cause for stress dosing prior to seeking medical attention?
 - What type, dose and route of parenteral GC was administered and the duration of administration?
 - What concomitant medications were administered?
 - What clinical laboratory results are available?
 - What AEs occurred?
 - What was the duration of stay if admitted to the hospital?
 - What was deemed to be the inciting factor leading to adrenal crisis?

For non-SAEs of adrenal insufficiency, all symptoms and findings on physical examination, vital sign collection and/or laboratory assessments leading to the diagnosis of adrenal insufficiency will be collected.

Adverse events or other conditions that lead to GC stress dosing should not be reported as AEs of adrenal insufficiency since the stress dosing is done to prevent, not treat, adrenal insufficiency. If an AE, such as an infection, results in GC stress dosing, the AE should be captured in the Adverse Event CRF. The following additional information will be collected in the patient diary during episodes of GC stress

dosing: start and stop date, concomitant medications, cause for stress dosing (e.g., infection, strenuous exercise, emotional stress, pain, surgery) and concurrent AEs. Adverse events resulting in stress dosing will be reported on the Adverse Event CRF.

7.3. Pharmacokinetic and Pharmacodynamic Assessments

A summary of blood draws for assessment of tildacerfont concentration and PD is presented in [Table 8](#).

Table 8. Tildacerfont Concentration and PD Sampling Time Points

Sample	Day 1	Week 2	Week 4	Week 8	Week 12	ET	F/U	EP (all visits)
PD markers (ACTH, 17-OHP, A4, testosterone, and 11KT)	Cohorts 1, 2, 4, 5, 6, & 7 (8 & 9 if indicated) Pre-dose ¹ 0.5-1.5 hr post-dose 3-5 hr post dose Cohort 3 Single sample ¹	Cohorts 1, 2, 4, 5, 6, & 7 (8 & 9 if indicated) Pre-dose ¹ 0.5-1.5 hr post-dose 3-5 hr post dose Cohort 3 Single sample ¹	Cohorts 1, 2, 4, 5, 6, & 7 (8 & 9 if indicated) Single sample ¹	Cohorts 1, 2, & 3 (1a if indicated) Single sample ¹	Cohorts 1, 2, & 3 (1a if indicated) Single sample ¹	All Cohorts	X ²	All Participants Single sample ¹
Tildacerfont concentrations	Cohorts 1, 2, 4, 5, 6, & 7 (8 & 9 if indicated) Pre-dose ¹ 0.5-1.5 hr post-dose 3-5 hr post dose Cohort 3 Single sample ¹	Cohorts 1, 2, 4, 5, 6, & 7 (8 & 9 if indicated) Pre-dose ¹ 0.5-1.5 hr post-dose 3-5 hr post dose Cohort 3 Single sample ¹	Cohorts 1, 2, 4, 5, 6, & 7 (8 & 9 if indicated) Single sample ¹	Cohorts 1, 2, & 3 (1a if indicated) Single sample ¹	Cohorts 1, 2, & 3 (1a if indicated) Single sample ¹	All Cohorts	X ²	All Participants Single sample ¹

Abbreviations: 11KT = 11-ketotestosterone, 17-OHP= 17-hydroxyprogesterone; A4 = androstenedione;

ACTH=adrenocorticotrophic hormone, corticotropin; F/U = follow-up; GC = glucocorticoid; EP= extension period;

PD=pharmacodynamics.

¹ These samples will be collected at approximately 8 AM (\pm 1 hour) before participants take any morning dose of GC (except for Cohorts 4 to 9, where sample will be collected prior to the tildacerfont morning dose and GC dose) and do not require fasting.

² As needed based upon abnormalities in prior visits.

Concentration of tildacerfont will be measured by a bioanalytical laboratory using validated methods.

Detailed instructions for the collection and handling of biological samples will be provided separately in the Laboratory Manual.

8. STATISTICAL CONSIDERATIONS

Statistical considerations are summarized here. A detailed description of statistical methods will be provided in the Statistical Analysis Plan (SAP).

8.1. Sample Size Determination

A sample size of up to approximately 70 participants (i.e., 15 adults, 30 children 11- to 17-years of age, and 25 children 2- to 10-years), will provide adequate data to assess the initial safety of tildacerfont in a pediatric and adult population and provide data to support the continued use of the PBPK model to determine pediatric dosing requirements in future studies.

8.2. Populations for Analyses

The Safety Population will include all participants who receive at least 1 dose of study drug and will be the primary analysis set for general and safety analyses.

The PK Population will include all participants in the Safety Population with at least 1 post-dose sample above the limit of quantification.

The PD Population will include all participants in the Safety Population with at least 1 evaluable post-baseline PD assessment.

8.3. Statistical Analyses

8.3.1. General Considerations

All individual data will be listed as measured. All statistical summaries and analyses will be performed using SAS software (SAS Institute Inc, Cary, North Carolina, USA).

All continuous variables will be presented using an 8-point descriptive summary (n, mean, standard deviation, median, interquartile range [25th percentile, 75th percentile], minimum, and maximum) by dose, as available. Categorical variables will be summarized by frequency and by percentage of participants in corresponding categories.

Any changes to the protocol-specified analyses will be pre-specified in the SAP before database lock.

8.3.2. Demographics and Baseline Characteristics

Listings and summaries will be provided for demographics (age, sex, ethnicity, and race) and baseline characteristics (weight, height, BMI, and BSA) for the Safety Population.

Baseline biomarkers and GC regimen will be summarized for the Safety Population.

8.3.3. Concomitant Medications

Prescription, OTC, and alternative medication use will be listed.

8.3.4. Safety Analyses

The Safety Population will be used for all safety analyses. Safety data will be listed by participant and summarized by adult equivalent dose levels (50, 100, 200 mg QD; and 200 mg, possibly 300 and/or 400 mg BID) using the frequency of event or descriptive statistical summaries, as appropriate. Listings and summary tables will be provided for AEs, clinical laboratory tests, vital signs, and ECG data. Urinalysis, psychiatric evaluations, concomitant medications, and physical examinations will be presented in listings only.

A DMC will review accumulating safety information by cohort. Refer to [Section 9.4.4](#) for information on the DMC.

8.3.4.1. Extent of Exposure

Dosing information for individual participants will be listed and include nominal dose (mg) and dose adjusted for body weight (mg/kg). Using dosing data, estimates of exposure to tildacerfont will be summarized. Dose discontinuations and reasons for study drug discontinuation will be listed and summarized.

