### 9.2.2 *Re-Enrolled, Different Cohort*

Re-enrolled subjects will have more than one set of cohort data. Therefore, the summary results by cohort will be summarizing these subjects by unique enrollment experience (per cohort) rather than per subject for summaries of disposition, protocol deviations and study drug exposure. Subjects who re-enrolled into two or more different cohorts will have multiple baseline values for safety and efficacy summaries – a set of baseline values for their first cohort experience, and a set of baseline values for each subsequent cohort experience.

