### *9.4.18 Adverse Events*

AEs are any untoward medical occurrence in a subject participating in a clinical trial with onset date from the signing of the informed consent/assent until the end of the follow up period.

TEAEs are defined as any AEs, regardless of relationship to study drug, which have an onset or worsening in severity on or after the first dose of study drug until 30 days after the final dose of study drug (Follow-up visit). For AEs that occur on the date of the first dose of study drug, the time of onset (before or after intake of study drug) will be specified and used for comparison. If a subject discontinues study drug but remains in the study, AEs with onset date after 30 days of last dose of study drug until the end of the follow up period will be considered post-treatment adverse events.

Related TEAEs are those reported by investigators as possibly related, probably related, or definitely related to the study drug.

AESIs are events that do not meet SAE criteria but must be monitored on an ongoing basis as defined in the Study Protocol Section 7.2.8 and identified in the AE eCRF page.

Serious AEs (SAEs) are defined in the Study Protocol Section 7.2.6 and identified in the AE eCRF page.

Dose-limiting toxicities (DLTs) are defined as a Common Terminology Criteria for Adverse Events (CTCAE) Grade 3 or higher TEAE that is also considered at least possibly related to study drug.

Suspected unexpected serious adverse reactions is an AE that is serious, related to study drug, and is not expected in the targeted disease (classic CAH).

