# **12 STUDY DRUG AND OTHER MEDICATIONS**

## **12.1 Exposure to Study Drug**

The drug accountability information, including number of tablets dispensed, number of tablets returned, and number of tablets lost or destroyed, nominal tildacerfont dose ([Section 9.4.15.1](#)), and dose adjusted for body weight ([Section 9.4.15.2](#)) will be presented in subject listings.

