The Study Protocol Section 8.3.4.1 states that “Using dosing data, estimates of exposure to tildacerfont will be summarized.” However, due to limitations in the collection of exposure and drug accountability data in this study, it is not possible to estimate tildacerfont exposure without making assumptions about the last dose date of the 12-week treatment period, the number of tablets dispensed, and the strength of the tablets dispensed. Therefore, information about exposure will only be listed on an individual basis as described in [Section 12.1](#).

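### The SAP replaces the protocol's exposure summary with listings although treatment duration could be summarised, and it sets no main-period last dose date for attributing TEAEs in extension entrants

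*Protocol*

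**What the plan says.** - **Protocol 8.3.4.1** commits to an aggregate description: "Using dosing data, estimates of exposure to tildacerfont will be summarized". It also calls for individual dosing listings in mg and mg/kg, and for discontinuations to be listed and summarised.
- **SAP Section 15** withdraws the aggregate part. It says that "it is not possible to estimate tildacerfont exposure without making assumptions about the last dose date of the 12-week treatment period", and adds two further items: "the number of tablets dispensed, and the strength of the tablets dispensed". Its conclusion is that "information about exposure will only be listed on an individual basis".
- **SAP 12.1** gives the content of those listings: "number of tablets dispensed, number of tablets returned, and number of tablets lost or destroyed", with nominal dose and dose per kg.
- **SAP 9.2.2** still counts re-enrolled participants by enrolment experience "for summaries of disposition, protocol deviations and study drug exposure", so it presupposes a by-cohort exposure summary.
- **SAP 9.4.18** defines a TEAE by onset or worsening "on or after the first dose of study drug until 30 days after the final dose of study drug". **SAP 14 and 14.1** tabulate these events by adult-equivalent dose level and by cohort.
- **SAP 4** sends the extension to a separate SAP. **SAP 11.1** keeps a tabulation of discontinuations and their reasons.

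**The concern.** Safety is the primary objective, and its tables are grouped by assigned adult-equivalent dose level. A reader comparing event frequencies between dose levels needs to know how long each group was on drug. This matters more here because planned treatment is 12 weeks in some cohorts and 4 weeks in others. The SAP plans no table of duration, adherence or cumulative dose.

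There is a second gap. Section 15 treats the last dose of the 12-week period as a date that would have to be assumed, and no other section supplies a rule for it. Without that date, nothing in this SAP separates main-period events from extension events in participants who continue. Some of them change dose on continuing, so events could be counted under a dose level the participant was no longer taking.

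**Working it through.** The plan gives no exposure figure to reproduce. The check compares sections and adds simple arithmetic.

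**1. Whom the date reason covers.** Cohort sizes are from Protocol Table 1.
- 12-week QD cohorts (1, 1a, 2, 3): 5 + 5 + 5 + 10 = 25.
- 4-week BID cohorts (4 to 9): 5 + 10 + 5 + 5 + 10 + 10 = 45.
- Total: 25 + 45 = 70, which matches the stated maximum.

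Only the first of the three reasons in Section 15 is tied to the 12-week period. It does not apply to 45 of 70 participants (64%). The tablet-number and strength reasons carry no such limit.

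**2. What duration needs.** Duration = last main-period dose date − first dose date + 1. Tablet count and strength do not enter.
- First dose: supervised in clinic on Day 1 (Protocol 3.1.2.2).
- Early stoppers: the discontinuation date goes on the eCRF (Protocol 6.1).
- Completers: the Week 12 or Week 4 visit date. SAP 9.4.4 already defines completing main treatment by those visits.

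**3. Scale of the visit-date assumption.** The main-period schedules allow ±3 days around Day 84 and Day 28 (Protocol Appendices 1 and 3).
- 3/84 = 3.6%.
- 3/28 = 10.7%.

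The actual visit date is recorded, so these figures show how far duration can depart from nominal within the window. They do not measure doses missed shortly before the visit.

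**4. Amount of treatment left unsummarised at full enrolment.** 25 × 12 + 45 × 4 = 300 + 180 = 480 planned participant-weeks.

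**5. Whether strength is a real obstacle to a mg-based summary.** Tablets are 25, 50 and 200 mg, with 1 to 6 taken daily (Protocol 5.2.2 and 5.2.4). For a once-daily dose:
- 75 mg can be 2 or 3 tablets;
- 150 mg can be 3, 4, 5 or 6;
- 200 mg can be 1, 4, 5 or 6.

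A count without strength therefore does not give mg taken or the number of tablets expected.

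**6. TEAE attribution in extension entrants.**
- Protocol 3.1.3: pending DMC review, Cohort 1 and 1a participants move to the 200 mg QD equivalent in the extension.
- Protocol 3.1: participants in Cohorts 4 to 9 may adjust dose in the extension.
- SAP 9.4.18 closes the window by the final dose, not by the last main-period dose.
- SAP 10.2 has date rules for adverse events and medications, but none for last dose.

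Read literally, the window for someone treated to Week 96 extends 96 − 12 = 84 weeks past the Week 12 visit, or 96 − 4 = 92 weeks past the Week 4 visit, plus 30 days.

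**The case against.** The strongest case on the other side has five parts.

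- **The change is disclosed and permitted.** Protocol 8.3.1 lets the SAP pre-specify changes before lock, SAP 4 makes the SAP governing, and Section 15 records this one with its replacement. That stands. But the need for an assumption is a reason to state it, and it does not rule out a duration summary.
- **Tablet strength is a genuine barrier.** This stands for mg taken and for adherence based on expected tablets, as step 5 shows. It does not touch duration.
- **Listings are enough in cohorts of 5 to 10.** They do show each early stopper, and discontinuations are still tabulated. They do not put time on drug beside pooled dose-level safety tables.
- **The extension has its own SAP.** It may set a cut-off, but it is not available here, and this SAP's TEAE definition contains none.
- **The last dose date is not said to be unusable.** A reader might infer that, if it cannot support an exposure summary, the TEAE window cannot be applied either. The documents do not support that. Section 15 says assumptions are needed and refers to the 12-week boundary, whereas the TEAE window uses the final dose. In extension entrants these are different dates.

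A reader might also infer that the low paediatric concentrations cannot be interpreted without an adherence table. That goes too far. Protocol 1.2.3 offers metabolism only as a possible cause. Post-dose Day 1 samples follow a supervised dose in every cohort except Cohort 3. The PK analysis is in a separate plan, which may use dosing history.

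**Conclusion.** The point holds in a limited form. The protocol's exposure summary is dropped for reasons that do not rule out a duration summary in any cohort, and one of those reasons does not apply to 45 of 70 planned participants. SAP 9.2.2 and Section 15 disagree. The primary safety tables would lack a summary of time on drug covering up to 480 planned participant-weeks, although individual listings and a discontinuation table remain.

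Separately, the absence of a main-period last dose date leaves TEAE attribution open for extension entrants whose dose changes. How many events this affects cannot be stated, because the documents do not give the number of entrants or of dose changes.

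The conclusion assumes full enrolment, recorded discontinuation and visit dates, and the end-of-treatment visit as an acceptable stand-in for the last main-period dose in completers. It is an inexpensive improvement to the SAP and does not show that the safety analysis is invalid.

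**What to change.** 1. In SAP 12.1, add a summary of treatment duration by adult-equivalent dose level and by cohort: main-period last dose date − first dose date + 1. Define the main-period last dose date as the recorded discontinuation date for early stoppers, and otherwise the Week 12 visit date (Cohorts 1 to 3) or Week 4 visit date (Cohorts 4 to 9).
2. In SAP 9.4.18, for extension entrants, end main-period TEAE attribution at that date. Assign later events to the extension analysis under the dose then taken.
3. Keep the true final dose date for follow-up and for the extension rows of Table 7. The main-period date should not be used there: the Week 96 window opens on Day 551, but with Table 7's Week 12 target it would close near Day 85 + 3 = 88.
4. Summarise tablet-count adherence only where both strength and count are known, and report the number of participants missing either.
5. Amend Section 15 accordingly and bring 9.2.2 into line with it.

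The cost is SAP wording, one more table and one stated assumption for completers. No new data collection is needed.
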